### ***Validating Self-report Measures:***

#### **Biochemical Outcome Measures (Baseline, Week 8, 20, 32).**

Following the procedures and recommendations outlined in a report on biochemical verification of abstinence, tests of plasma **%CDT and GGT** will be used as an unbiased, biological outcome variable that will be used to validate self-report measures (Anton, Lieber, & Tabakoff, 2002) (Martínez-Raga et al., 2002).

### ***Measures and Assessments:***

#### **Individual Difference Measures (Baseline).**

- A Demographics Questionnaire will be used to collect information on age, sex, marital status, SES, occupation, income, education, and race.
- The Stages of Change Readiness and Treatment Eagerness Scale (SOCRATES) will be used to measure individual differences in motivation at baseline.
- Drinking History is measured with 12 items assessing lifetime drinking history such as current drinking, age of onset, and number of previous of attempts to quit/reduce drinking.
- A Smoking History Questionnaire will be used to collect information on frequency and quantity of nicotine use and will be used to determine whether the treatment groups differ on nicotine consumption.
- A Cannabis Self-Treatment questionnaire will be used to better characterize our population in case participants are self-treating with cannabis.

#### **Self-Report Outcome Measures (Baseline, Week 4, 8, 20, 32).**

- Heavy Drinking Days (HDD), Drinks per Drinking Day (DDD), and Percent Days Abstinent (PDA) as well as any comorbid drug use (e.g., tobacco use) will be obtained at each assessment using the Timeline Follow Back (TLFB), which is a calendar-based assessment of daily alcohol and drug use (Sobell et al., 1979). The TLFB has been shown to have good psychometric characteristics among a variety of drinker groups and can generate variables that provide a wide range of information about an individual's drinking (e.g., pattern, variability, and magnitude of drinking). HDD is the primary behavioral outcome that will be analyzed. However, secondary outcome measures of interest will also be collected.
- The Impaired Control Scale – Failed Control (ICS-FC) is a 25-item scale that is used to measure the severity of alcohol dependence with respect to dimensions such as impaired control over drinking, awareness of compulsion to drink, etc. (Heather, Booth, & Luce, 1998).
- The Alcohol Dependence Scale (ADS) has been used widely and found to have excellent predictive value with respect to DSM diagnosis (Kivlahan, Sher, & Donovan, 1989).
- The Pennsylvania Alcohol Craving Scale (PACS) is a 5-item measure of craving that will be completed at baseline and at each follow-up session to provide a measure of craving (Flannery, Volpicelli, & Pettinati, 1999). In a recent study, the PACS was found to be a

slightly better predictor of drinking as compared to the OCDS and AUQ (Flannery, Poole, Gallop, & Volpicelli, 2003).

- The Drug Use Questionnaire assesses individual behavior with regard to frequency and quantity of drug use. This measure will be used to assess whether smoking and drug use behavior changes during the course of clinical trial.
- The Beck Depression Inventory-II (BDI-II) consists of 21 scaled statements designed to assess symptoms of depression, with a coefficient alpha of .91 (Beck, Steer, & Carbin, 1988) The BDI-II will be administered at baseline and at last follow-up to examine changes in comorbid depression and covary baseline differences if necessary.
- The Beck Anxiety Inventory (BAI; Beck et al., 1988) consists of 21 items, each describing a common symptom of anxiety. The items are summed to obtain a total score that can range from 0 to 63. The BAI will be administered to examine comorbid anxiety and covary baseline differences if necessary.
- The Five Facet Mindfulness Questionnaire (Baer et al., 2006) will determine the extent to which MBRP increases mindfulness practice as a proximal mediator of the effects of the intervention. These data will be used as a manipulation check.
- The extent to which patients engage in key aspects of mindfulness will be collected using the 10 item Mindfulness Practice Questionnaire (e.g., [name], Lustyk, & [name], 2013) on a weekly basis.
- The CHIME (Bergomi, Tschacher, & Kupper, 2015) consists of three items and will determine the number of minutes of mindfulness practice per week each patient is currently engaging in. Minutes of current meditation practice will be calculated using the following compound variable: (weekly frequency x average session duration). The data will be used to co-vary for patients who are already engaging in frequent mindfulness meditation practice at baseline if necessary.
- The Multidimensional Personality Questionnaire (Tellegen, 1982, Tellegen & Waller, 2008) consists of 18 True/False items of statements describing negative emotionality and stress reaction. The questionnaire will be administered to examine comorbid negative emotionality and used to co-vary baseline differences if necessary.
- The Ruminative Response Scale (Treynor, Gonzalez, & Nolen-Hoeksema, 2003) consists of 22 items scoring how often the patient engages in ruminative thinking associated with depression. The data will be used to examine comorbid negative emotionality and used to co-vary baseline differences if necessary.
- The Effortful Control Scale Derryberry & Rothbart, 1988, Evans & Rothbart, 2007) consists of 35 items that measure the degree to which the patient exhibits behavioral control. The data will be used to co-vary baseline differences in behavioral control if necessary.
- The Drinking Motives Questionnaire (Cooper, 1994, Kuntsche et al., 2006, Young-Wolff et al., 2009) consists of 20 items used to assess patients' varying motives for drinking alcohol. The Drinking Motives Questionnaire will be used to assess whether motives for drinking alcohol change from baseline following treatment.
- Alcohol use will be evaluated with a variation of the measure used by White and Labouvie (1989). First, participants will be asked if they have ever had an alcoholic drink (with instructions that define one alcoholic drink as “one beer, one glass of wine, or one serving of hard liquor either by itself or in a mixed drink”). Those (likely well over 90%) who

answer that they have previously had alcohol before will be asked to rate: (1) their frequency of use in the last three months on a 9-point scale ranging from “never” to “every day”, (2) their typical quantity of drinks in one sitting on a 10-point scale ranging from “no drinks” to “more than 20 drinks”, and (3) their frequency of getting drunk when drinking in the past three months on a 5-point scale ranging from “never” to “always.”

- The AUDIT (Saunders, Aasland, Babor, De La Fuente & Grant, 1993) is used to detect less severe problem drinkers and addresses both current problems (problems within the last 3 months) and problems across an individual’s lifetime. The AUDIT consists of ten questions that cover such domains as alcohol consumption, drinking behavior, adverse psychological reactions, and alcohol-related problems.
- Participants will be asked about their engagement in any 12-step programs (Tonigan, Miller & Conners, 1997), psychological services for alcohol and other problems, and use of other self-help materials. At baseline, participants will be asked about lifetime engagement in treatment. Because this study will be recruiting a population of heavy drinkers, it will be important for us to know whether or not any of our participants have previously received treatment for alcohol abuse. In future analyses, this information (e.g., prior treatment history) will be used as a covariate.
- The AUQ (Bohn et al., 1995) will be used to assess craving. The AUQ consists of eight items related to urge drink that are rated on a 7-point Likert scale with the extremes anchored by "Strongly Disagree" and "Strongly Agree." The AUQ has demonstrated internal consistency and reliability.
- The ImpSS (Zuckerman, 1996) consists of 19 items measuring impulsivity and sensation seeking that may predict responses to alcohol and drug problems. The sum of the symptoms endorsed is a proxy measure of dependence.
- The Fruits and Vegetable Screener is a 10-item measure that was developed by the National Cancer Institute to assess how many times in the previous month subjects consumed different types of fruits and vegetables, including portion size questions for every food item. This measure was shown to be a useful estimate for obtaining median intakes of fruit and vegetable servings in U.S. populations (Thompson et al., 2002). Fruit and vegetable consumption has been shown to influence inflammation (e.g., Holt et al., 2009), and dietary factors have also been linked with epigenetic changes (see Hardy & Tollesbol, 2011). Thus, the inclusion of this measure allows fruit and vegetable consumption to be controlled for in inflammation and epigenetic analyses.
- The single-item, self-rated diet quality measure (Loftfield et al., 2015) consists of a single question asking “In general, how healthy is your overall diet?” Participants can respond with (1) excellent, (2) very good, (3) good, (4) fair, or (5) poor. The item is significantly associated with variation in objective measures of dietary intake ( $P<.001$ ).
- The VAEQ assesses levels of voluntary exercise ([name] and Rocheleau, 2002). Participants indicated how frequently they engaged in exercise activities in the past 3 months and past week. The exercise composite score used in these analyses was composed of 4 items: (i) “In the past 3 months, what is the average number of days per week that you engaged in aerobic exercise?” (ii) “In the past 3 months, what is the average number of total minutes per week that you engaged in aerobic exercise?” (iii) “In the past week, how many days did you engage in aerobic exercise?” and (iv) “In the past week, what is the total number of minutes that you engaged in aerobic exercise?” This measure has been used to quantify exercise participation in our previous alcohol studies (Karoly et al., 2013).

Given that exercise may impact inflammation (see Woods, Vieira, & Keylock, 2009) and epigenetics (see Ntanasis-Stathopoulos, Tzanninis, Philippou, & Koutsilieris, 2013), this measure (either alone or in combination with the Godin, see below) will allow us to control for exercise behavior in inflammation and epigenetic analyses.

- The Godin Leisure-Time Exercise Questionnaire (QLTEQ; Godin & Shephard, 1985) is used to generate ‘activity scores’ based on how many separate times (occasions) in a typical week participants engage in mild, moderate, or vigorous exercise for more than 15 minutes of their leisure time. The three levels of intensity are defined as follows: (1) mild exercise, defining features include, slightly elevated heartbeat, slightly elevated breathing rate (able to carry on a conversation effortlessly); (2) moderate exercise, defining features include accelerated heartbeat, moderately elevated breathing rate (able to carry on a conversation), and mild physical exhaustion; and (3) vigorous exercise, defining features include rapid heartbeat, heavy breathing (difficult or unable to carry on conversation), and physical exhaustion. Participants will be asked to answer how many separate times they engaged in mild, moderate, and vigorous intensity exercise over the past week (for each data collection time point). This measure could be used alone or in combination with the VAEQ to control for exercise participation in inflammation analyses.
- The PSS (Cohen, Kamarck, & Mermelstein, 1983) is a 14-item scale that measures (1) the degree to which situations in someone’s life are perceived as stressful. Stress is a known correlate of substance use and abuse and it will be crucial for us to obtain a measure of our participants’ perceived stress levels, which may be associated with inflammatory processes (e.g., Hart & Kamm, 2002) and epigenetic changes (see Eric J Nestler, 2012). Thus, this measure will be used to control for stress in epigenetic and inflammation analyses.
- The PSQI (Buysse, Reynolds, Monk, Berman, & Kupfer, 1989) is a 19-item self-report scale that measures sleep quality over the past month. The 19 self-related items are combined to form seven “component” scores, each of which has a range of 0-3 points. In all cases, a score of “0” indicates no difficulty, while a score of “3” indicates severe difficulty. The seven component scores are then added to yield one “global” score, with a range of 0-21 points. In the present study, it will be important to control for sleep duration and/or quality, given that sleep is known to be associated with inflammation (e.g., Patel et al., 2009) and epigenetic factors (see Qureshi & Mehler, 2014). Thus, component scores, global scores and single item scores could all potentially be used as covariates in later analyses of these data. Scores from this measure will be included as covariates in inflammation and epigenetic analyses.
- The Leisure-Time Categorical Item (L-Cat) is a single item comprised of six descriptive categories ranging from inactive to very active (Kiernan, Schoffman, Lee, Brown, Fair, Perri, & Haskell, 2013). Each category consists of 1–2 sentences describing common activity patterns differing in frequency, intensity, duration, and types of activities, thus encompassing content validity (van Poppel, Chinapaw, Mokkink, van Mechelen, & Terwee, 2010). Respondents pick the category best describing their activity during the past month. It assesses national activity recommendations as well as multiple clinically relevant categories below and above recommendations, and incorporates critical methodological principles that enhance psychometrics (reliability, validity, sensitivity to change).
- The Pain Interference item bank is from the National Institutes of Health (NIH) and is part of the Patient Reported Outcomes Measurement Information System (PROMIS). The Pain Interference SF-8a, is a 8-item short-form questionnaire that measures the self-reported

consequences of pain on relevant aspects of one's life. This includes the extent to which pain hinders engagement with social, cognitive, emotional, physical, and recreational activities (Amtmann et al., 2010).

- Emotion Regulation Questionnaire (ERQ) is a 10-item scale that is designed to assess individual differences in the habitual use of two emotion regulation strategies: cognitive reappraisal and expressive suppression (Gross, John, 2003).

Because of the COVID-19 situation and the remote nature of the study, we will not be collecting the Neurocognitive data:

### **Neurocognitive NIH Toolbox Measures (Baseline & Week 8).**

- **Flanker Inhibitory Control & Attention Test:** Tests inhibitory control and attention. The participant focuses on a particular stimulus while ignoring other stimuli. Five arrows are displayed in the middle of the screen, each pointing left or right. The participant selects the arrow that matches the middle arrow in the sequence.
- **Dimensional Change Card Sort Test:** Measures cognitive flexibility and attention. Two target pictures are presented that vary along two dimensions (e.g., shape and color). Participants are asked to match one of the two bottom cards to the card displayed at top, by either color or shape.
- **Pattern Comparison:** Measures processing speed. The test takes less than 90 seconds and requires participants to discern whether two side-by-side pictures are the same or not.
- **Picture Sequence Memory Test:** Tests episodic memory. Participants are asked to reproduce the sequence of pictures that is shown on the screen.
- **Picture Vocabulary Test:** A measure of receptive vocabulary administered in a computer-adaptive test (CAT) format. Participant matches picture with spoken word.
- **List Sorting Working Memory Test:** Participants have to say back the list of images they are given.

### ***Power Analysis:***

#### **Sample Size Requirements.**

Sample size was selected to permit analysis of the hypotheses at a two-tailed alpha of .05 and power level of at least .80 following Cohen (Cohen, 1988). G\*Power 3.0.3 (Erdfelder, Faul, & Buchner, 1996) was utilized for some power calculations, while Monte Carlo simulation strategies formed the basis of our power analysis for the mediational model ([name], Schmiege, & Broaddus, 2007; Mackinnon & Dwyer, 1993).

#### **The impact of attrition.**

It is anticipated that some attrition will occur in this population, though we do not anticipate differential attrition by condition. A conservative estimate of 20% attrition over the course of data collection is assumed. Recently published evidence suggests an attrition rate of approximately 20% for other trials. In our own previous trials, we have seen attrition of around 20%. Thus, sample size will need to be increased by 20% over minimum requirements. After final attrition has been calculated, pretest differences on alcohol use and problems will be compared among individuals who finished the study versus those who did not and by condition, to determine whether these two groups differed in

systematic ways and whether these differences were related to treatment condition.

With respect to attrition during the follow-up period, all participants will update their address and phone number as well as the name and number of an individual who always knows how to reach them at every visit. The project coordinator will also contact each patient in between follow-up visits.

### **Power for Specific Aim 1 - Detecting Treatment Effects on Alcohol Use Outcomes.**

The analyses of treatment effects will proceed via random coefficient regression utilizing a 2 (**Treatment**: 8 weeks of MBRP vs. 8 weeks of RP) x 5 (**Time**: Baseline, 4, 8, 20, 32 weeks) mixed general linear model. The primary outcome variable tested will be heavy drinking days (HDD), consistent with previous MBRP trials ([name] et al., 2014). Secondary analyses will explore related outcomes such as drinks per drinking day, scores on the ICS, and liver function tests, with appropriate control of Type I error. In each model, the key effect of interest will be the treatment X time interaction. Given the effect sizes in previous trials (small  $d=.23$  or  $f<.10$  to moderate  $d=.45$  or  $f=.20$ ), we conservatively estimate a small effect size (e.g.,  $f=.10$ ). A mixed model testing the between (treatment) X within (time) subjects interaction with a total of 180 participants (90 per treatment group) will give us well over .90 power, assuming alpha of .05 and a correlation of approximately .50 between repeated assessments. Given that we expect 20% attrition over the course of the trial, we will initially recruit ~226 participants.

### **Power for Specific Aim 2 - Detecting Treatment Effects on Putative Molecular Mechanisms.**

As reviewed above, the effect sizes for the impact of MBIs (and thus likely MBRP) on inflammatory biomarkers and epigenetic regulation ranged from moderate to large. Thus, for tests of the hypotheses under Specific Aim 2, that there will be treatment effects on both inflammatory markers and epigenetics, the effect sizes are in all cases larger than our estimated effects of treatment on outcomes. Thus, 226 participants are more than adequate for Hypothesis 2 of Specific Aim 2. In terms of Hypothesis 3 of Specific Aim 2, there are no data available to estimate the size of the direct effects of MBRP on cue-elicited BOLD activation or on network connectivity. With 226 participants, we will be able to detect a direct effect as small as  $d=.38$  (a small to moderate effect) on change in BOLD activation and network connectivity as a result of MBRP versus RP.

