#### **Specific Aim 2 - Detecting Treatment Effects on Molecular Mechanisms.**

The effect of the treatment on methylation and inflammation (HYPOTHESIS 2) will be analyzed with one 2 (**Treatment:** 8 weeks of MBRP vs. 8 weeks of RP) x 5 (**Time:** Baseline, 4, 8, 20, 32 weeks) mixed multivariate general linear model with methylation outcomes of DRD2, SLC6A3, and DBH and a second model with peripheral inflammation outcomes of IL-6, IL-8, and TNF $\alpha$ . The effect of the treatment on cue-elicited BOLD activation and network connectivity (HYPOTHESIS 3) will be analyzed with a 2-way multivariate analysis of variance (MANOVA; **Treatment:** 8 weeks of MBRP vs. 8 weeks of RP) with BOLD activation in the accumbens, caudate, putamen, and anterior cingulate regions as separate outcomes in the same analysis, and a second MANOVA with network connectivity

The image part with relationship ID rid9 was not found in the file.

in the RECN and LECN as the outcomes. Note, again, that FIML estimation will be used to allow full utilization of available data in an intent to treat framework. It is also possible that the treatments are equally effective on drinking outcomes, and thus we will not see a differential effect of treatment on the mediators. Yet it is still important to know whether levels of methylation or inflammation post-treatment have any impact on changes in

neurocognitive outcomes. Thus, the test of Specific Aim 3 is still critical, even in the case that both treatments are equally effective on both the mediators and drinking outcomes.

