### **MRI Scan I**

All subjects who are eligible will undergo a structural scan, using a Siemens 3T Trio, followed by an fMRI scan that involves alcohol cue exposure. Female participants will be asked to take a

pregnancy test free of charge and must have a negative result in order to continue with participation in the study. Female participants may opt out of the urine pregnancy test and sign a waiver (one of the standard INC MRI scanning forms) indicating they understand that the risks associated with MRI and unborn fetuses is unknown and that they are confident that they are not currently pregnant.

The research assistant will go over the contraindications for fMRI screening form again with the participant to ensure that eligibility has not changed since the phone screen; if there is any question that a participant might not be safe to go into the scanner the appointment will be cancelled and rescheduled if possible.

Prior to going into the MRI scanner, the MRI technologist on duty will ask participants to remove all jewelry and metal objects from their pockets. Participants will be required to change into scrubs to prevent any possible risk from metallic objects or decorations in their clothing. Eligible participants will be escorted to a changing room where they will be asked to change into the hospital scrubs provided, and to lock up their belongings in the locker.

A trained MRI technician will position participants in the scanner and ensure that all safety procedures are followed. In an MRI scan, the subject lies down on a table and is placed into a long donut-shaped magnet. A specially designed coil will be placed around the head to provide better images (as is done with standard clinical examinations). As the MRI scan is performed, the subject will hear loud rattling and knocking noises that are normal for a MRI scan.

During the scanning session, we will acquire anatomical images for subsequent analysis as well as functional images during an alcohol cue task. The alcohol cue task compares the taste of an individual's favorite alcoholic beverage with a sweet, appetitive control taste (litchi juice). Subjects will be administered 1 ml of each beverage through Teflon tubing that is attached to a computer controller gustometer, over each 24-second trial. The total amount of the alcoholic beverage is only 1 ml (less than a teaspoon).

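### The detectable imaging effect for Hypothesis 3 (d=.38) is stated at the 226 recruited; at the 180 the plan expects to keep it is about d=.42, or .40 to .42 under FIML

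*Combined protocol and SAP*

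**What the plan says.** - Sample Size Requirements sets a two-tailed alpha of .05 and a "power level of at least .80".
- The impact of attrition: "A conservative estimate of 20% attrition over the course of data collection is assumed", and the sample is to be enlarged accordingly.
- Power for Specific Aim 1 computes power "with a total of 180 participants (90 per treatment group") and continues: "Given that we expect 20% attrition over the course of the trial, we will initially recruit ~226 participants".
- Power for Specific Aim 2 says of Hypothesis 3 that "there are no data available to estimate the size of the direct effects of MBRP" on BOLD activation or connectivity. It therefore gives a detectable effect instead: "With 226 participants, we will be able to detect a direct effect as small as" d=.38, for change between MBRP and RP.
- The Aim 2 analysis section plans one MANOVA with "BOLD activation in the accumbens, caudate, putamen, and anterior cingulate regions as separate outcomes in the same analysis", a second with the two executive control networks, and FIML for missing data.
- MRI Scan I: "All subjects who are eligible will undergo a structural scan". No number of scanned participants is given.

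**The concern.** The two power sections use 226 differently. For Aim 1 it is the number recruited so that about 180 remain. For Hypothesis 3 it is the number analysed. An analysis of change draws its information mainly from participants with both scans, so the Hypothesis 3 figure holds only if almost nobody is lost.

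The plan has no prior estimate of the imaging effect. The detectable d is therefore the figure a reader would use to judge whether a null imaging result is informative, and it should be stated at a sample the plan expects to have. The Aim 3 power section shows how: it gives power at 150, 200 and 226 participants.

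**Working it through.** **Inputs from the plan.** Two-sided alpha .05; power .80; equal allocation, 113 per arm (Specific Aim 1); d=.38; 20% attrition; 180 retained. Check: 180/.8 = 225 and 226 × .8 = 180.8, so 226 is the inflated number.

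**Formula.** Two-sample comparison of one standardised change score: noncentral t with N−2 degrees of freedom and noncentrality d × √(N/4).

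**Reproducing the plan's figure.** At N=226 the noncentrality is .38 × √56.5 = 2.86. Power is .812 and the effect detectable at power .80 is d=.374. This matches the stated d=.38 with nobody lost. Power of .80 at d=.38 needs 220 participants, so 226 − 220 = 6 losses (2.7%) are tolerated. The plan expects about 45 (226 − 180.8).

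**Complete cases after loss.** The 20% is the plan's figure; the smaller losses are assumptions. At N=180 the noncentrality is .38 × √45 = 2.55.

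| Loss by second scan | N | Power for d=.38 | Detectable d |
|---|---|---|---|
| none | 226 | .81 | .374 |
| 5% | 214.7 | .79 | .384 |
| 10% | 203.4 | .77 | .395 |
| 20% | 180 | .72 | .420 |

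**With FIML.** Participants with only a baseline scan stay in the model. With m of n per arm scanned twice and scan-rescan correlation r (not in the documents; 0 to .8 assumed), the effective number per arm is 2(1−r) / [(1−r²)/m + (1−r)²/n]. For m=90 and n=113:

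- r=0: 2 / (1/90 + 1/113) = 100.2
- r=.8: .4 / (.36/90 + .04/113) = 91.9

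Power for d=.38 is then .76 to .73 and the detectable d is .40 to .42. At 10% loss power is .79 to .77. At 5% loss it is about .80 to .79.

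**With the baseline scan as covariate.** If the follow-up scan is adjusted for the baseline scan, d on the change-score scale is multiplied by √(2/(1+r)), with N−3 degrees of freedom. At 180:

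| Assumed r | Power for d=.38 | Detectable d |
|---|---|---|
| .3 | .88 | .34 |
| .5 | .83 | .36 |
| .7 | .79 | .39 |

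**The planned MANOVAs.** These use Hotelling's T² with noncentrality (N/4) × D², where D² is the squared Mahalanobis distance between arms. At 180, with d=.38 on each affected outcome and an assumed common correlation:

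| Pattern | Four outcomes | Two outcomes |
|---|---|---|
| One affected, correlation 0 | .49 | .61 |
| One affected, correlation .3 to .7 | .58 to .92 | .66 to .90 |
| All affected, correlation .3 to .7 | .85 to .62 | .81 to .69 |

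Multivariate power can therefore lie on either side of the single-outcome .72.

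**The case against.** The best defence is that the sentence is conditional and true: with 226 analysable participants d=.38 is detectable. No target effect was set for Hypothesis 3, so power of .72 at d=.38 breaches no stated requirement; at 180 power is still .80, only at d=.42. This is right as far as it goes. The formula is correct, and the fault is that its N disagrees with the plan's own attrition assumption.

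FIML recovers part of the loss and makes the shortfall trivial at 5%, but at 20% it does not restore .80 anywhere in the assumed range. Baseline adjustment could: .80 at d=.38 is reached at r=.3 and r=.5, and just missed at r=.7. The Aim 2 analysis section does not state that adjustment, and the power section speaks of change, so the gain cannot be credited to the plan as it stands.

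A reader might infer that the imaging hypothesis is badly underpowered or that more patients are needed. The documents do not support that. A detectable d of .42 still lies between the small (.23) and moderate (.45) effects cited for Aim 1, Aim 1 set the sample size, and Hypothesis 3 is not the primary outcome analysis. Nor can the low MANOVA values be read as the power of the planned tests, because they depend on correlations and effect patterns that the plan does not give.

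**Conclusion.** The point holds, at modest size. At the plan's own 20% loss, d=.38 has power .72 in complete cases and .76 to .73 under FIML, against .81 at 226. The detectable d moves from the stated .38 to about .42 (.40 to .42 under FIML). The figures rest on one outcome, unadjusted change, equal arms and, for FIML, an assumed scan-rescan correlation of 0 to .8.

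Two features of the plan affect which figure applies:

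- **Scanned number.** 180 is likely a ceiling. MRI-ineligible participants are still randomised (Baseline Session), participants may opt out of the cue exposure (Exposure to Alcohol, under Management of Risks), and the temporary remote phase collects no MRI.
- **Scan date.** The second scan is at week 32 in MRI Data Collection, Resting State Connectivity and Follow-up Assessment II. It is at week 8 in the Aim 3 mediational analysis and the MRI row of the measures table. At week 32 the full 20% applies; an earlier scan would plausibly lose fewer.

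The design and the sample size stand.

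**What to change.** 1. In Power for Specific Aim 2, say that with 180 participants with both scans (90 per arm) the detectable effect on change in a single imaging outcome is about d=.42, or about .40 to .42 under FIML with the assumed correlation stated. Add the detectable d at the expected number with two usable scans.
2. If the follow-up scan is to be analysed with the baseline scan as covariate, say so in the Aim 2 analysis section and quote the gain with its assumed correlation (at 180, d=.34 to .39 for r=.3 to .7). Say also that the figure is for one outcome, not for the four- and two-outcome MANOVAs.
3. Reconcile the week 8 and week 32 statements of the second scan, since the date determines the loss that applies.

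The cost is one reworded sentence, at most one sentence on the model and one reconciled date. No patients are added; the stated figure becomes slightly less favourable.
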